10.4 Appendix 4: Contraceptive Guidance and Collection of Pregnancy Information

Contraception Guidance for women of childbearing potential: (see Inclusion criterion 3, Section 5.1)

The investigator or a designated associate is requested to advise the participant how to achieve highly effective birth control in women of childbearing potential. Highly effective (failure rate of less than 1% per year) contraception methods include:

- Combined (estrogen and progesterone containing: oral, intravaginal, transdermal) and progesterone-only (oral, injectable, implantable) hormonal contraception associated with inhibition of ovulation.
- Intrauterine device (IUD) or intrauterine hormone-releasing system (IUS).
- Bilateral tubal occlusion or vasectomized partner (provided that the partner is the sole sexual partner and has received medical assessment of the surgical success).
- Sexual abstinence (reliability to be evaluated in relation to the duration of the clinical trial and the preferred and usual lifestyle of the participant).

Periodic abstinence (e.g., calendar, ovulation, symptothermal, or postovulation methods) and withdrawal are not acceptable methods of contraception.

Collection of Pregnancy Information

Male participants with partners who become pregnant:

- The investigator will attempt to collect pregnancy information on any male participant's female partner who becomes pregnant while the male participant is in this study. This applies only to male participants who receive study intervention.
- After obtaining the necessary signed informed consent from the pregnant female partner directly, the investigator will record pregnancy information on the appropriate form and submit it to the sponsor within 24 hours of learning of the partner's pregnancy. The female partner will also be followed to determine the outcome of the pregnancy. Information on the status of the mother and child will be forwarded to the sponsor. Generally, the follow-up will be no longer than 6 to 8 weeks following the estimated delivery date. Any termination of the pregnancy will be reported regardless of fetal status (presence or absence of anomalies) or indication for the procedure.

10.5 Appendix 5: Abbreviations

ADT	Androgen deprivation therapy
AE	Adverse event
ALT	Alanine aminotransferase
AR	Androgen receptor
AST	Aspartate aminotransferase
AUC(0–24)	Area under the curve from time zero to 24 hours after dosing
BCRP	Breast cancer resistance protein
BFI	Brief Fatigue Inventory
bid	Twice daily
BUN	Blood urea nitrogen
CFR	Code of federal regulations
CI	Confidence interval
CIOMS	Council for International Organizations of Medical Sciences
C _{max}	Maximal plasma exposure
CNS	Central nervous system
CONSORT	Consolidated Standards of Reporting Trials
COWA	Controlled Oral Word Association
CPM	Counts per minute
CRF	Case report form
CRPC	Castration-resistant prostate cancer
CT	Computed tomography
CTCAE	Common Terminology Criteria for Adverse Events
CYP	Cytochrome P450
DMC	Data monitoring committee
DRE	Disease-related event
DSM-IV	Diagnostic and Statistical Manual of Mental Disorders
ECOG	Eastern Cooperative Oncology Group
eCRF	Electronic case report form
F876L	Mutation of phenylalanine at position 876 to leucine
FACT-Cog	Functional Assessment of Cancer Therapy – Cognitive
FAS	Full analysis set
GCP	Good clinical practice
GMP	Good manufacturing practice
GnRH	Gonadotropin-releasing hormone
GPP3	Good publication practice 3
HDPE	High density polyethylene
HIPAA	Health Insurance Portability and Accountability Act
HIV	Human immunodeficiency virus
HVLT-R	Hopkins Verbal Learning Test – Revised
HVLT-R DR	Hopkins Verbal Learning Test – Revised Delayed Recall
HVLT-R RECOG	Hopkins Verbal Learning Test – Revised Delayed Recognition
HVLT-R TR	Hopkins Verbal Learning Test – Revised Total Recall
IB	Investigator’s brochure
ICF	Informed consent form
ICH	International Council for Harmonisation of Technical Requirements for Pharmaceuticals for Human Use
ICMJE	International Committee of Medical Journal Editors
IEC	Independent Ethics Committee

IMP	Investigational medicinal product
IRB	Institutional Review Board
IUD	Intrauterine device
IUS	Intrauterine hormone-releasing system
IWRS	Interactive web response system
KPS	Karnofsky Performance Scale
LHRH	Luteinizing hormone-releasing hormone
LPLV	Last patient last visit
MCH	Mean corpuscular hemoglobin
MCID	Minimal clinically important difference
MCV	Mean corpuscular volume
MedDRA	Medical Dictionary for Regulatory Activities
MFS	Metastasis-free survival
MRI	Magnetic resonance imaging
NCI	National Cancer Institute
NCI-CTCAE	National Cancer Institute Common Terminology Criteria for Adverse Events

## Abbreviations

AE	Adverse event
AESI	Adverse Event of Special Interest
ALT/SGPT	Alanine aminotransferase/ Serum glutamic-pyruvic transaminase
AST/SGOT	Aspartate aminotransferase/Serum glutamic-oxaloacetic transaminase
BFI	Brief Fatigue Inventory
bid	Twice daily
BUN	Blood urea nitrogen
CFR	Code of federal regulations
CI	Confidence interval
CMH	Cochran-Mantel-Haenszel
COWA	Controlled Oral Word Association
CRF	Case report form
CPM	Count per minute
CRPC	Castration-resistant prostate cancer
CTCAE	Common Terminology Criteria for Adverse Events
eCRF	Electronic case report form
FACT-Cog	Functional Assessment of Cancer Therapy – Cognitive
FAS	Full analysis set
GCP	Good clinical practice
HVLT-R	Hopkins Verbal Learning Test – Revised
HVLT-R DR	Hopkins Verbal Learning Test – Revised Delayed Recall
HVLT-R RECOG	Hopkins Verbal Learning Test – Revised Delayed Recognition
HVLT-R TR	Hopkins Verbal Learning Test – Revised Total Recall
ICF	Informed consent form
ICH	International Council for Harmonization
IRB	Institutional Review Board
IWRS	Interactive web response system
KPS	Karnofsky Performance Scale
MCH	Mean corpuscular hemoglobin
MCID	Minimal clinically important difference
MCV	Mean corpuscular volume
MedDRA	Medical Dictionary for Regulatory Activities
NCI	National Cancer Institute
OS	Overall survival
PCWG	Prostate Cancer Working Group
PHQ-9	Patient Health Questionnaire-9
PSA	Prostate-specific antigen
PT	Preferred term
RBC	Red blood cell
RCI	Reliable change index
SAE	Serious adverse event
SAP	Statistical analysis plan
SoA	Schedule of activities
SOC	System Organ Class
SPPB	Short Physical Performance Battery
TEAE	Treatment-emergent adverse event
TMTA/TMTB	Trail Making Test Part A/B
TUG	Timed Up and Go
ULN	Upper limit of normal
WBC	White blood cell

## 1.0 Introduction

This Statistical Analysis Plan (SAP) describes analyses and data presentations for Bayer HealthCare Pharmaceuticals Protocol 20609. It provides details of the analysis populations, derived variables, and statistical methods to be used in the analyses and reporting of safety and efficacy data.

The purpose of the SAP is to ensure the credibility of the study findings by specifying the statistical approaches to study data analyses. This SAP will be finalized and signed prior to the clinical database lock for the final analyses. All statistical analyses detailed in this SAP are conducted using SAS statistical software (version 9.4 or higher).

### 1.1 Study Documents Used in the Preparation of this Document

The following documents were used in preparation of this SAP:

Study Document	Approval Date
Clinical Study Protocol	06 JUN 2019
20609-1180 Annotated eCRF Approval	17Sep2020
1180 Rave Annotated CRF Review	17Oct 2019

## 2.0 Objectives and Endpoints

**Table 1 Objectives and Endpoints**

Objectives	Endpoints
Primary	

The primary objective of this study is to compare the effects of treatment with darolutamide vs. enzalutamide on physical function as assessed by the Timed Up and Go (TUG) test in participants with castration-resistant prostate cancer (CRPC).
	
Proportion of participants with a worsening in TUG time during the 24-week period from baseline. Worsening is defined as an increase of at least 1 second from baseline, using the best TUG time out of the measured assessments during study visits. (The minimum clinically important difference [MCID] in TUG time is 1 second (Davies et al. 2016)) [1].

Secondary	

The secondary objectives of this study are to:
 
 
• Compare the effects of treatment with darolutamide vs. enzalutamide on physical function, as assessed by the TUG test at 12 and 24 weeks, and by 52 weeks.
 
• Compare the effects of treatment with darolutamide vs. enzalutamide on physical function as assessed by Short Physical Performance Battery (SPPB) test at 12 and 24 weeks, and by 24 and 52 weeks.
 
• Assess the effects of treatment with darolutamide vs. enzalutamide on daily activity as assessed by accelerometry at 12 and 24 weeks, and by 24 and 52 weeks.
 
• Compare the effects of treatment with darolutamide vs. enzalutamide on cognitive function as assessed by Hopkins Verbal Learning Test-Revised
 
	
Physical Function:
 
 
• Proportion of participants with an increase of at least 1 second in TUG time at 12 and 24 weeks and during the 52 weeks from baseline, using the best TUG time out of the measured assessments during study visits.
 
• Time to worsening (increase of at least 1 second) in TUG time.
 
• Proportion of participants with a worsening in SPPB total score at 12 and 24 weeks and during the 24 weeks and 52 weeks from baseline. Worsening is defined as one point worsening in SPPB total score from baseline.
 
 
Daily Activity:
 
 
• Mean change from baseline in daily physical activity at 12 and 24 weeks, and during the 24 weeks and 52 weeks from baseline.
 
• Mean change from baseline in accelerometer-assessed proportion of time spent in light to vigorous physical activity (light physical activity defined as 100<AC per minute<760 and moderate-to-vigorous activity (≥760 AC per minute), at 12 and 24 weeks, and during the 24 weeks and 52 weeks from baseline.
 
 
Cognitive Function:
 
 
• Proportion of participants with a decline in cognitive function during the 24 weeks and 52 weeks from baseline, as assessed by HVLt-R, TMT, and COWA. See Table 4 for the definition of decline for each test.
 

Objectives	Endpoints

(HVLt-R), Trail Making Test (TMT), Controlled Oral Word Association (COWA), and Functional Assessment of Cancer Therapy – Cognitive questionnaire (FACT-Cog).
 
 
Compare the effects of treatment with darolutamide vs. enzalutamide on fatigue as assessed by the Brief Fatigue Inventory (BFI).
 
Compare the effects of treatment with darolutamide vs. enzalutamide on depression as assessed by the Patient Health Questionnaire-9 (PHQ-9).
 
Evaluate safety, including AEs of special interest (AESI), of participants treated with darolutamide vs. enzalutamide.
 
Evaluate the effect of treatment with darolutamide or enzalutamide on prostate-specific antigen (PSA), survival status, and exposure.
 
	
 
Proportion of participants with a decline using a selected domain of FACT-Cog. Decline is defined as a decrease of >10 points during the 24 weeks and 52 weeks from baseline.
 
 
Fatigue:
 
 
Proportion of participants with a worsening of fatigue during the 24 weeks and 52 weeks from baseline. Worsening is defined as an increase of at least 1 point in worst level of fatigue from baseline by 24 weeks and 52 weeks (based on item 3 of the BFI).
 
Proportion of participants with an increase of at least 1 point in fatigue interference by 24 weeks and 52 weeks from baseline (based on items 4A-F of the BFI).
 
 
Depression:
 
 
Proportion of participants with a worsening in scores in the PHQ-9 during the 24 weeks and 52 weeks from baseline. Worsening is defined as an increase of at least 1 point in worst level of depression from baseline by 24 weeks and 52 weeks.
 
 
Safety
 
 
All treatment emergent AEs (TEAEs), serious adverse events (SAEs), and AEs leading to study intervention discontinuation.
 
AEs of interest listed in section 5.5.3.
 
 
Exposure and other:
 
 
Treatment exposure of the study intervention (defined as investigational intervention, protocol; Darolutamide or Enzalutamide) including time on treatment.
 
Dose reductions of study intervention.
 
Time to PSA progression (as per Prostate Cancer Working Group [PCWG3] criteria).
 
Survival status.
 

### 3.0 Study Design

#### 3.1 Overall Study Design

This randomized, open-label, multicenter, Phase 2b study is designed to evaluate physical function, including balance and daily activity, in

[figure not shown]
participants with CRPC, treated with darolutamide (or enzalutamide in randomized phase). It will also evaluate, safety, cognitive function, fatigue, and survival.

The study consists of two phases, a lead-in phase and a randomized phase. In the lead-in phase, approximately 30 participants will be treated with darolutamide. The lead-in phase analysis will be performed when the last participant in the lead-in phase has been on the study for at least 24 weeks, unless the participant discontinued due to lost to follow-up, withdrawal, or death. The decision to move to the randomized phase of the study will be conditional on the findings of the lead-in phase which will be reviewed with the members of the steering committee. Findings of the lead-in phase will determine feasibility to move on or not with a randomized phase. If determined feasible and decided to proceed with the randomized phase, the appropriate endpoint and the time point and time frame of evaluation of the endpoint for a randomized part of the study will be chosen and the sample size will be reassessed.

In the randomized phase, approximately 120 additional participants will be randomized in a 1:1 ratio to receive either darolutamide (600 mg twice daily) or enzalutamide (160 mg once daily) in the randomized phase of the study. Randomization will be stratified by age (<75, ≥75 years).

The endpoints used in this study are novel in a way that, decline in physical function, will be evaluated using objective measures such as TUG, SPPB, and accelerometry, therefore, the lead-in phase has been added to be able to assess compliance and the variability of the endpoints and overall feasibility of the study execution. The randomized phase of the study will start only after a decision is made based on the findings from the primary analysis of the lead-in phase as described above.

**Figure 3-1: Study Periods**

CRPC = castration-resistant prostate cancer; N = number of participants; R = randomization. Randomization will be stratified by age (<75 vs ≥75 years).

### 3.2 Blinding and Unblinding

This is an open-label study; blinding techniques are not required.

No formal interim analyses are planned in this study and a Data Monitoring Committee will not be utilized. However, a Steering Committee will provide strategic direction, guidance and oversight for the study. This committee will meet approximately once a year or as required to keep track of issues and the progress of the study's implementation and activity.

### 3.3 Randomization and Stratification

Following the primary evaluation of the lead-in phase, approximately 120 additional patients will be randomized in a 1:1 ratio to receive either darolutamide (600 mg twice daily) or enzalutamide (160 mg once daily) using an Interactive Web Response System. Randomization will be stratified by age (<75, ≥75 years).

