5.1 Inclusion Criteria

Participants are eligible to be included in the study only if all of the following criteria apply:

Age

1. Participant must be 18 years of age inclusive or older at the time of signing the informed consent.

Type of Participant and Disease Characteristics

2. Participants who have:
 - Histologically or cytologically confirmed adenocarcinoma of prostate, CRPC defined by disease progression despite ADT and may present as either a confirmed rise in serum PSA levels (as defined by PCWG3), the progression of pre-existing disease, and/or the appearance of new metastases. Metastatic and non-metastatic CRPC patients will be eligible.
 - KPS performance status of ≥ 80
 - Blood counts at screening: hemoglobin ≥ 9.0 g/dL, absolute neutrophil count $\geq 1500/\mu\text{L}$, platelet count $\geq 100,000/\mu\text{L}$
 - Screening values of serum alanine aminotransferase (ALT) and/or aspartate aminotransferase (AST) $\leq 2.5 \times$ upper limit of normal (ULN), total bilirubin $\leq 1.5 \times$ ULN, creatinine $\leq 2.0 \times$ ULN
 - Life expectancy of at least 1 year

- Eligible for treatment with enzalutamide (only for the randomized phase)

Sex

3. Male

Contraceptive use by men should be consistent with local regulations regarding the methods of contraception for those participating in clinical studies.

Sexually active participants, unless surgically sterile, must agree to use condoms as an effective barrier method and refrain from sperm donation during study treatment and for 3 months after the end of the study treatment. Participants who are sexually active with a female partner of childbearing potential, unless surgically sterile, must agree to ensure that an additional form of contraception is also used. See Appendix 4 (Section 10.4) for contraceptive guidance for women of childbearing potential.

Informed Consent

4. Capable of giving signed informed consent as described in Appendix 1 (Section 10.1) which includes compliance with the requirements and restrictions listed in the informed consent form (ICF) and in this protocol

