### 5.4.3 Other

Additional subgroup analyses will be performed, as specified below. Time to PSA progression and OS will be explored across baseline characteristic subgroups.

- Age group (< 75 vs. ≥ 75 years)
- Number of prior systemic life-prolonging anticancer therapies (1 vs. ≥ 2)

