### 5.5.1 Primary Endpoint Analyses

The primary variable in this study is the proportion of participants with a worsening in TUG time during the 24-week period from baseline, using the best TUG time out of the measured assessments during study visits (two or

three assessments). Worsening is defined as an increase of at least 1 second in TUG time from baseline.

The proportion of participants with a worsening in TUG time and the (exact) 95% CIs will be summarized by treatment arm. A comparison between treatment arms will be made using Cochran-Mantel-Haenszel (CMH) test adjusting for Age (<75, ≥75). A sensitivity analysis will be provided by replacing missing TUG times with ≥ 1 second increase. Primary endpoint (worsening in TUG) analysis will be performed by age (<75, ≥75), metastatic state (nmCRPC, mCRPC), Pain (yes, no pain), and opioid use (yes, no opioid use). Information on pain and opioid use will be retrieved from an examination of medical history and prior medication CRFs.

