## **5.5.2 Secondary Endpoints Analyses**

### **Physical function**

- Proportion of participants with a worsening in TUG time from baseline at 12 and 24 week study visits, and at any time up to 52 weeks will be summarized.
- TUG time (secs) and percent change from baseline will also be summarized by metastatic/non-metastatic CRPC status, pain (yes, no pain), and opioid use (yes, no opioid use).
- At each assessment, status of TUG time will be summarized as the categories of improved, stable or worsened.
- Time to worsening in TUG time will be defined as time from randomization (or time from first dose for participants in the lead-in phase) to the first date a participant had a worsening. Time to worsening in TUG time will be summarized using Kaplan-Meier methodology, and a comparison between the two arms in the randomization phase will be made using a two-sided, stratified log-rank test, stratified by Age (<75, ≥75). The hazard ratio as well as its 95% CI will be presented using a stratified Cox regression model. An unstratified analysis will also be performed. The Kaplan-Meier plots will be provided for both stratified and unstratified analyses.
- Similar to the primary endpoint, the proportion of participants with a decline of at least 1 point in SPPB total score at 12 and 24 week study visits and at any time up to 24 and 52 weeks will be summarized. SPPB

will be analyzed by age (<75, ≥75), metastatic state (nmCRPC, mCRPC), Pain (yes, no pain), opioid use (yes, no opioid use).

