### Daily Activity

- Descriptive statistics on mean change and percent change from baseline in daily activity, measured as counts per minute (CPM), will be provided for both lead-in at 12 and 24 weeks and randomization phase at 12, 24 and 52 weeks. Subjects must provide at least 2 out of 7 days of data prior to the visit, each day containing ≥10 awake hours, to be considered eligible for analysis. For each epoch, counts from the X, Y and Z axes will be converted to a single measure per the vector magnitude =

$$\sqrt{(axis\ 1)^2 + (axis\ 2)^2 + (axis\ 3)^2}$$

CPM for each valid day is defined as ‘awake wear-filtered total vector magnitude counts’ divided by ‘awake wear minutes’. A subject’s CPM at each visit is the average of daily CPM.

- CPM will also be analyzed by age (<75, ≥75), metastatic state (nmCRPC, mCRPC), pain (yes, no pain), and opioid use (yes, no opioid use) in both phases. In the randomization phase, model-based least squares means on percent change from baseline in CPM will be reported for treatment group, adjusting for baseline CPM, age (<75, ≥75), metastatic state (nmCRPC, mCRPC), pain (yes, no pain) and opioid use (yes, no opioid use).
- Because of the skewed nature of CPM data, summary statistics will also be provided for log-transformed CPM. For summary statistics by visit, calculations are done on the log scale, and then back-transformed at the end. For % change from baseline, the back-transform for (LS)mean (95% CI) =  $100 \times [\exp(\text{LS)mean change from baseline (95\% CI) in natural logarithm}) - 1]$ .
- For the randomization phase, treatment arms will be compared at each visit using 2-sample t-test, mean change difference (SE), 95% CI and p-value of darolutamide vs. enzalutamide will be provided.
- The percentage of time at each visit that CPM fall into the following categories will be summarized for the lead-in phase: Sedentary (0-99), Light (100-1951), Moderate (1952-5724), Vigorous (5725-9498), Very vigorous (9499-∞). Also mean change and percentage change from

baseline will be summarized for percentage of time spent in each of the aforementioned categories.

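### Age is the only stratum in the randomisation and in the Timed Up and Go comparisons; adding metastatic state, which is already recorded, would be a cheap improvement

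*SAP*

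**What the plan says.** - Eligibility (Protocol 5.1): "Metastatic and non-metastatic CRPC patients will be eligible".
- Randomisation (SAP 3.3): "Randomization will be stratified by age (<75, ≥75 years". Protocol 1.1, 4.1 and 4.1.1 say the same.
- Primary test (SAP 5.5.1): "A comparison between treatment arms will be made using Cochran-Mantel-Haenszel (CMH) test adjusting for Age (<75, ≥75".
- Time to TUG worsening (SAP 5.5.2, Physical function): "stratified log-rank test, stratified by Age (<75, ≥75", with a stratified Cox model and an unstratified analysis alongside. Protocol 9.4.2 does not name age for the CMH and log-rank tests. It ties them to whatever strata the interactive web response system (IWRS) holds.
- Metastatic state is tabulated at baseline (SAP 5.3.6). It is a reporting factor for the primary endpoint (SAP 5.5.1): "Primary endpoint (worsening in TUG) analysis will be performed by age (<75, ≥75), metastatic state (nmCRPC, mCRPC", together with pain and opioid use. SAP 5.5.2 uses the same factors for the Short Physical Performance Battery and for accelerometer counts per minute (CPM). The randomised-phase CPM model goes further, "adjusting for baseline CPM, age (<75, ≥75), metastatic state (nmCRPC, mCRPC), pain (yes, no pain) and opioid use (yes, no opioid use".
- Other time-to-event endpoints (SAP 5.4.3): "Time to PSA progression and OS will be explored across baseline characteristic subgroups". The factors listed are age and number of prior therapies. SAP 5.4.2 rules out a formal comparison of the arms on efficacy.
- Protocol 4.1 and 4.2 leave the design of the randomized phase to be settled after the lead-in. Stratification is not named as an item for that review, but the wording is broad enough to cover it.

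**The concern.** The SAP adjusts one secondary model for metastatic state and reports three functional measures by it, but neither balances nor adjusts for it in the comparison that decides the trial. With 120 men, balance on an unstratified binary factor is left to chance. If metastatic men worsen more often on TUG, an arm with more of them looks worse for a reason unrelated to the drug. The age-only CMH would not remove that difference. A breakdown of TUG by metastatic state would make it visible but would not give an adjusted overall result.

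**Working it through.** **1. The plan's own figure.** Inputs from SAP 3.4: 120 randomised 1:1, 20% against 40% worsening, one-sided alpha 10%, 10% drop-out. Evaluable: 120 × 0.9 = 108, or 54 per arm.

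z = (0.20 × √54 − 1.2816 × √(2 × 0.30 × 0.70)) / √(0.20 × 0.80 + 0.40 × 0.60) = (1.470 − 0.831) / 0.632 = 1.01, so power is 84.4%. The stated 85% is reproduced.

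**2. Chance of imbalance.** The documents give no metastatic share, so 30% and 50% are assumed (70% gives the same result as 30%). Of 120 men, K are metastatic. The number X in one arm of 60 is hypergeometric, and the difference in share is (2X − K)/60. Its SD is (2/60) × √(60 × q × (1 − q) × 60/119), with q = K/120.

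| Share | SD of difference | 10 points or more | 15 points or more | 20 points or more |
|---|---|---|---|---|
| 30% (K = 36) | 8.4 points | 32% | 7% | 3% |
| 50% (K = 60) | 9.2 points | 36% | 10% | 4% |

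A difference of exactly six men (10 points) counts in the first probability. Strictly more than 10 points has probability 16% and 20%.

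**3. Shift in the arm difference.** Shift = imbalance × gap in worsening risk between the states. The documents give no gap, so 10 to 30 points is assumed. A 10-point imbalance shifts the difference by 0.10 × (10 to 30) = 1 to 3 points, and a 20-point imbalance by 2 to 6 points, against a design difference of 20.

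**4. Behaviour of the two tests.** Set-up: 100,000 simulated trials per setting, 54 evaluable per arm, 22 of 54 aged 75 or over in each arm (assumed, and unrelated to risk), metastatic state not stratified at randomisation. Worsening is 30% in both arms under the null and 20% against 40% under the alternative. The rule is CMH z > 1.2816.

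Averaged over randomisations, 50% metastatic:

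| Gap | Type I error, age only | Type I error, age × metastatic | Power, age only | Power, age × metastatic |
|---|---|---|---|---|
| 0 | 9.9% | 10.1% | 84.2% | 84.1% |
| 10 points | 9.7% | 10.0% | 84.0% | 84.2% |
| 20 points | 9.8% | 10.1% | 84.1% | 85.6% |
| 30 points | 9.6% | 10.0% | 83.9% | 87.4% |

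The power gains are 0.2, 1.4 and 3.5 points for gaps of 10, 20 and 30 (0.3, 1.3 and 2.8 at a 30% share). They come from the adjustment alone, because the simulated randomisation is not stratified by metastatic state.

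Given an unfavourable imbalance of 6 men (11 points) or 10 men (19 points) out of 54, 50% metastatic. The type I columns have the excess of metastatic men on enzalutamide, and the power columns have it on darolutamide:

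| Gap | Imbalance | Type I error, age only | Type I error, age × metastatic | Power, age only | Power, age × metastatic |
|---|---|---|---|---|---|
| 10 | 11 | 11.7% | 9.9% | 81.0% | 84.4% |
| 10 | 19 | 13.5% | 10.0% | 78.3% | 83.6% |
| 20 | 11 | 14.0% | 10.0% | 77.6% | 85.4% |
| 20 | 19 | 18.5% | 10.1% | 71.8% | 84.8% |
| 30 | 11 | 16.2% | 9.9% | 73.7% | 87.3% |
| 30 | 19 | 23.9% | 10.1% | 64.1% | 86.7% |

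Imbalances in the other direction offset these, which is why the averages in the previous table stay near 10% and 84%.

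**The case against.** The strongest reply is that nothing is wrong. Stratifying on one factor and testing on that factor is valid, and the first simulation table confirms it. The size is also small against sampling noise. At a 20-point gap, a 10-point imbalance moves the difference by 2 points, while the standard error is √(0.16/54 + 0.24/54) = 8.6 points, so the shift is less than a quarter of one standard error. Over repeated trials, chance imbalance contributes an SD of 0.092 × 20 = 1.8 points, or (1.8/8.6)², under 5% of the sampling variance. All of this stands, and it limits the point to an improvement.

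A second reply is that pain and opioid use appear beside metastatic state in the SAP, so the same logic would make them strata too. This stands in part: the SAP gives no reason to rank one above the others. But four binary factors give 16 cells for 120 men. Pain and opioid use also have to be extracted from medical-history and prior-medication records (SAP 5.5.1), whereas metastatic state is a disease classification already needed for the prior-therapy limits in Protocol 5.2.

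Three stronger readings are tempting, and the documents do not support them.

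- A reader might infer that the SAP declares metastatic state prognostic. It never says so. It uses the state as a covariate and a reporting factor.
- A reader might infer that PSA progression and survival comparisons are left uncorrected. SAP 5.4.2 plans Kaplan-Meier estimates per arm and no formal comparison, so there is no test to correct. What remains is a missing line in an exploratory subgroup list.
- A reader might extend the point to adverse events such as fractures. These are summarised descriptively, and the documents offer nothing from which to size an effect.

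Nor is the comparison within the metastatic or non-metastatic subgroup confounded by metastatic state. At worst, the arm sizes within a subgroup are uneven.

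**Conclusion.** The point holds as a cheap improvement, not as an error. The age-only analysis is valid on average. What it lacks is protection in the one trial that will be run. With a 30 to 50% metastatic share, about one trial in three has an imbalance of 10 points or more, and the primary comparison would carry that imbalance unadjusted. Adjustment holds type I error at about 10% whatever the imbalance. On average it adds about 0 to 4 points of power for a gap of 10 to 30 points, and it costs almost nothing if the gap is zero.

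The metastatic share and the gap are both assumptions. The lead-in will report TUG by metastatic status (SAP 9.0, Table 17.2), so the sponsor can check them. With about 30 men, all on darolutamide, it will give a rough share and only a very imprecise gap.

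**What to change.** At the reassessment after the lead-in, and before the first randomisation:

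1. Add metastatic state (nmCRPC, mCRPC) as a second binary IWRS factor. Four strata for 120 men average 30 each, or 15 per arm. Edit Protocol 1.1, 1.2, 4.1 and 4.1.1, and SAP 3.1 and 3.3.
2. In SAP 5.5.1 and 5.5.2, replace age alone with age × metastatic state as the strata of the primary CMH and of the log-rank and Cox analyses of time to TUG worsening. Protocol 9.4.2 refers to IWRS strata for the CMH and log-rank tests, so there the new factor carries over without further change.
3. If the IWRS is left as it is, pre-specify the adjusted analyses alone. Protocol 9.4.2 would then need to name metastatic state, because it would not be an IWRS stratum. This keeps the power gain shown above but gives no balance by design.
4. Add metastatic state to the exploratory subgroups for time to PSA progression and overall survival in SAP 5.4.3.

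The cost is one IWRS setting and wording changes. The sample size does not change and no new data are collected. The downside is slightly smaller strata, which matters if one state turns out to be rare among men in either age group. The lead-in share should be looked at before the factor is fixed.
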